11.3.1. Part A Analysis Timing and Decision Rules

The primary analysis for part A will be performed when 11 relapses (confirmed on imaging) have been observed. This analysis will focus on miRNA sensitivity, feasibility, adherence and acceptability. If $\geq 10/11$ relapses were identified by positive miRNA results, at the same time or prior to diagnosis on imaging, and there are no concerns based on secondary endpoints, the trial will proceed to Part B.

An updated analysis of the Part A cohort will take place when 21 relapses have accrued, to provide additional reassurance early on during Part B recruitment. A final analysis will take place when all Part A participants have been followed up for 36 months at which time 28 relapses are expected to have been observed. Further secondary endpoints, including specificity and lead time will be analysed at this time. Results of these analyses will be reviewed by the Independent Data Monitoring Committee (IDMC), in the first instance, and they will make recommendations about continuation of Part B. For continuation of Part B (and in accordance with the design, as described in 11.1.1), it is expected that at least 19 of the first 21 relapses and at least 26 of the first 28 relapses will be identified on miRNA (at the same time or before detection on imaging). However, IDMC recommendations will also consider secondary endpoint data available at this time.

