1.1.2. Surveillance in early-stage disease

In current practice, most stage I seminoma patients are managed with active surveillance following surgery. This involves periodic cross-sectional imaging (typically 3-7 scans over 5 years), alongside tumour markers and clinical assessment. Around 10-20% of patients relapse, treatment is very successful, and survival approximately 100%¹¹. In dysgerminoma, current international guidelines for early stage, completely resected stage I disease unanimously recommend surveillance, but approaches differ – even within the UK – and have not been prospectively evaluated^{12,13}. Current biomarkers, HCG and AFP, have a low rate of sensitivity for seminoma relapse (at most 30%) and LDH lacks specificity, so is also of limited value¹⁰. As the main relapse site is in the para-aortic lymph nodes, in the absence of a reliable biomarker, current surveillance relies on imaging with CT or MRI. For the NHS, this is expensive and resource intensive; for patients, having scans is time-consuming and can induce anxiety¹⁴. Furthermore, CT scans expose patients to significant, cumulative diagnostic radiation¹⁵. Although there has been a move towards use of MRI in the UK following the TRISST trial results¹⁶, this is limited by capacity.

Thus, there is a clear unmet need to strike the right balance between early detection of recurrent disease (in a minority of patients) and the intensity of radiologic surveillance. Reflecting this, the 2019 James Lind priority setting exercise for TYA cancers included identifying follow-up schedules which cause the least psychological and physical harm, whilst ensuring relapses are detected early¹⁷. A blood-based biomarker with good sensitivity for relapse detection, which might replace some or all imaging, is highly desirable. Consultation with patients has identified the potential benefits including increased sensitivity and safety, reduced time for testing and results, practical benefits and reduced anxiety¹⁴. For the NHS, there would be financial benefits¹⁸ and increased imaging capacity for other patients. Furthermore, if the biomarker can detect recurrence earlier, this could reduce the need for subsequent, intensive chemotherapy (such as BEP; bleomycin,

etoposide and cisplatin). More relapses might be treated with local therapies or single-agent carboplatin, bringing further patient benefits and cost-savings for the NHS.

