2.2. Secondary Objectives**Part A:**

- To demonstrate high specificity of miRNA for relapse detection in this setting
- To demonstrate feasibility and acceptability to patients of miRNA monitoring in this setting
- To quantify the lead time (extent to which relapse diagnosis can be bought forward) associated with miRNA monitoring when compared with standard surveillance

Part B:

- To demonstrate cost-effectiveness of miRNA monitoring compared with standard surveillance
- To demonstrate reduced use of imaging and subsequent impact on radiation exposure with miRNA monitoring compared with standard imaging-based surveillance
- To further evaluate acceptability to patients of miRNA monitoring in this setting
- To quantify anxiety, fear of recurrence and health-related quality of life for patients managed with the two different approaches to surveillance
- To understand any impact on disease outcomes and subsequent treatment associated with use of miRNA monitoring in place of standard imaging
- To understand the risk-benefit balance of a miRNA monitoring approach (when compared to standard surveillance) from the perspective of different stakeholders, including patients

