Participants found to have raised markers (according to one or more of the criteria below) should have all tumour markers repeated within 1-4 weeks. If persistently elevated, this should be further investigated as per section 7.4.2:

- β -HCG>4 IU/L
- AFP >10 (if \leq 10 at baseline) OR increase of >25% above baseline (where >10 at baseline)
- LDH >1.2 x upper limit of normal

[figure not shown]
Any abnormal finding on physical examination should be followed up as per local practice.

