11. STATISTICAL CONSIDERATIONS

11.1. Statistical Design, Intervention Allocation and Sample Size Justification

11.1.1. Part A Statistical Design

Part A will use a phase II, A'Hern single arm design³⁷ with all participants receiving the intervention (miRNA monitoring) alongside standard surveillance imaging.

The aim is to demonstrate that miRNA sensitivity exceeds a pre-specified threshold and, hence, sample size is driven by the number of relapses. The sample size is based on the combined cohort (seminoma and dysgerminoma), since differences are not anticipated, and this will allow more timely progression to Part B.

Sensitivity of miRNA for relapse detection is expected to be at least 95% based on previous studies³⁰. Sensitivity >75% is deemed appropriate to warrant further study (i.e. progression to Part B) and, ultimately, the aim is to demonstrate that sensitivity exceeds 85%. For this phase II evaluation, a one-sided alpha of 0.2 will be used. The higher “false positive” risk associated with using a higher alpha than might traditionally be used will facilitate a timely decision regarding initiation of the Part B which will provide a confirmatory evaluation. Subsequent analyses of the Part A cohort, when more relapses have been observed, will achieve greater precision in estimating sensitivity.

In order to have 80% power to show sensitivity >75%, with one-sided alpha of 0.2, a total of 11 relapses need to be observed. If at least 10 of these are correctly identified on miRNA at the same time or before being identified on imaging, a sensitivity $\leq 75\%$ could be excluded. Two further analyses will be performed when 21 and 28 relapses have occurred with the aim of showing sensitivity >80% and >85% respectively, requiring at least 19 of 21 and at least 26 of 28 relapses to be detected on miRNA. Power for both of these analyses (using one-sided alpha of 0.2) will be >80%. Calculations were performed using Stata version 17.0.

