11.2. Endpoint Definitions

11.2.1. Part A Primary Endpoint

The primary endpoint for Part A is sensitivity of miRNA for relapse detection, defined as the number of relapses detectable on miRNA testing before or at the same time as detection on imaging (or via other components of standard surveillance) as a proportion of the total number of relapses identified via standard investigations. In all cases, date of detection will be taken to be the date of the sample collection or imaging/investigation (rather than the date the results were available) and a 2-week window will be allowed from detection on imaging/standard investigations to allow for scheduling of miRNA testing sometimes occurring after imaging. Detection on miRNA requires a positive result according to lab-specific normal ranges, and the date of sample collection will be taken to be the date of relapse detection.

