11.2.2. Part A Secondary Endpoints

The following secondary endpoints will be evaluated during part A:

- Lead time for relapse detection on miRNA, defined as time between relapse detection on miRNA (date sample taken) and relapse detection on imaging (date of scan).

- Specificity of miRNA for relapse detection, defined as number of non-relapsing participants (based on imaging) whose miRNA levels remained negative (or indeterminate) throughout the follow-up period, as a proportion of all non-relapsing participants.
- Time from blood draw for miRNA testing to miRNA results being available to the clinical team (and participant), and the number (proportion) of results available within 2 weeks.
- Adherence to miRNA testing, defined as the number of samples taken for miRNA testing as a proportion of all scheduled tests; numbers of tests performed more than a 4-week window either side of the schedule time point and number of samples that could not be analysed will also be reported.
- Adherence to imaging schedules defined as the number of attendances for imaging as a proportion of all scheduled imaging; the number of scans performed; numbers of scans performed more than a 4-week window either side of the schedule time point will also be reported.
- Patient-reported acceptability of miRNA monitoring without routine surveillance imaging (using a trial-specific questionnaire based on a validated, generic instrument for evaluating acceptability of healthcare interventions^{35,36}).

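### For relapses first flagged by a routine marker, the primary endpoint uses one reference date while the progression rule and lead time use another (the scan)

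*Protocol*

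**What the plan says.** The protocol defines the reference for miRNA in two ways.

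- **Primary endpoint (sections 3.1 and 11.2.1).** A relapse counts as detected if miRNA is positive "before or at the same time as detection on imaging (or via other components of standard surveillance"). Detection is dated by the sample or investigation, and 2 weeks are allowed after detection by imaging or another standard investigation.
- **Progression rules (sections 11.1.1 and 11.3.1).** Part B opens if at least 10 of 11 "relapses were identified by positive miRNA results, at the same time or prior to diagnosis on imaging". The 19/21 and 26/28 rules in 11.3.1 are also tied to imaging only.
- **Analysis set (section 11.3.2).** Sensitivity includes relapses confirmed on imaging that have a miRNA test within 2 weeks of detection on imaging.
- **Lead time (section 11.2.2; likewise 3.2 and 11.3.3).** It is "defined as time between relapse detection on miRNA (date sample taken) and relapse detection on imaging (date of scan"). The objective in section 2.2 is "To quantify the lead time (extent to which relapse diagnosis can be bought forward) associated with miRNA monitoring when compared with standard surveillance".

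The follow-up pathway separates the two dates. Under section 7.3, participants with a raised marker "should have all tumour markers repeated within 1-4 weeks". Only a persistent rise leads on to MRI or CT, and section 7.4.2 asks for a repeat miRNA test at that stage. On how often markers show relapse, section 1.1.2 says that HCG and AFP "have a low rate of sensitivity for seminoma relapse (at most 30" per cent).

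**The concern.** When routine imaging is the first sign of relapse, the two references coincide and nothing is at stake. They separate when a marker is raised first. The marker must then be confirmed and a scan arranged, so the scan can fall more than 2 weeks after the first raised sample. Two things follow.

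1. **Sensitivity.** If miRNA is negative when the marker rises but positive at the repeat taken with the scan, the endpoint definition can call the relapse a miss while the progression rule calls it a hit. The scan reference gives miRNA more time and a further sample.
2. **Lead time.** If miRNA is positive on the day the marker is raised, it is credited with the whole interval to the scan, although standard surveillance flagged the relapse that same day.

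The first bears on opening a randomised phase with an arm that has no routine imaging. The second bears on a secondary endpoint whose stated purpose is a comparison with standard surveillance as a whole. Neither concerns which relapses enter the denominator; the issue is the date against which miRNA is judged.

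**Working it through.** **1. Reproduce the design.** Section 11.1.1 states: "In order to have 80% power to show sensitivity >75%, with one-sided alpha of 0.2, a total of 11 relapses need to be observed". It also states: "Sensitivity of miRNA for relapse detection is expected to be at least 95% based on previous studies". With X ~ Binomial(11, p),

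P(X ≥ 10) = 11·p^10·(1 − p) + p^11.

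- p = 0.75: 0.155 + 0.042 = 0.197 (alpha).
- p = 0.95: 0.329 + 0.569 = 0.898 (power).

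Eleven is the smallest number of relapses that meets both limits. The later rules also hold: 19/21 against 80% gives alpha 0.179 and power 0.915; 26/28 against 85% gives 0.187 and 0.837. The thresholds are sound.

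**2. One relapse decides.** The lower limit of the exact 60% confidence interval is 0.650 for 9/11 and 0.751 for 10/11. Only the second excludes 75%.

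**3. Classify one relapse under each reference.** Week 0: marker raised, miRNA negative. Week 4: marker confirmed. Week 6: scan positive and repeat miRNA positive. The 2-week wait for the scan is an assumption.

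| Reference | Detection date | Window ends | Result |
|---|---|---|---|
| 11.2.1, dated at first raised marker | week 0 | week 2 | miss |
| 11.2.1, dated at confirming marker | week 4 | week 6 | hit, at the limit |
| 11.3.1, scan | week 6 | n/a | hit |

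Section 11.2.1 does not say which marker sample counts. Even with the confirming sample, a longer scan wait turns the hit into a miss.

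**4. Lead time for one relapse.** Marker and miRNA are both positive at week 0 and the scan is D weeks later. Under 11.2.2 lead time is D weeks. Against standard surveillance, dated at that first raised marker, it is 0. What makes up D depends on the visit. At real-time visits a positive miRNA itself triggers the scan (section 7.4.2), so D is result turnaround plus booking, and the 1-4 week marker repeat does not add to it. At 9, 15, 21 and 42 months the miRNA result is not returned, so the scan waits for the marker repeat.

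**5. How many relapses are exposed.** Let m be the share of relapses that are marker-first. The protocol does not give it. I take 10% to 30%, using the section 1.1.2 ceiling on HCG/AFP sensitivity as the top and assuming that LDH and examination add none.

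- Lead time: m × 11 = 1.1 to 3.3 relapses; m × 28 = 2.8 to 8.4.
- Sensitivity: the relapse must also be miRNA-negative at the marker date. With sensitivity s assumed equal in marker-first and other relapses, the expected number is 11 × m × (1 − s). At m = 0.30 this is 11 × 0.30 × 0.25 = 0.8 for s = 0.75, and 11 × 0.30 × 0.05 = 0.2 for s = 0.95. These are upper counts, because each must also turn positive by the scan.

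**6. Probability of a go.** Let q be the share of exposed relapses that turn positive by the scan. If sensitivity is 0.75 on the endpoint's reference, then on the scan reference it is 0.75 + m × 0.25 × q.

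| m | q | Sensitivity, scan reference | P(go) |
|---|---|---|---|
| 0 | n/a | 0.750 | 0.197 |
| 0.10 | 0.5 | 0.7625 | 0.224 |
| 0.20 | 0.5 | 0.775 | 0.254 |
| 0.30 | 0.5 | 0.7875 | 0.287 |
| 0.30 | 1.0 (extreme) | 0.825 | 0.402 |

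Both m and q are assumptions.

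**The case against.** **The rule is shorthand for the endpoint.** Sensitivity is formally defined in 11.2.1, and section 11.3 says the Part A analyses are only outlined. This does not settle it. Every counted relapse is confirmed on imaging, so if detection always meant the scan, the bracketed words in 11.2.1 would do nothing. The imaging-only wording also recurs in 11.1.1, 11.3.1 and 11.3.2, and nothing says which governs. A SAP would have to choose between two protocol definitions.

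**An imaging reference is defensible.** miRNA is meant to replace scans, and routine markers stay in both Part B arms (section 7). That is a fair reason to report a scan-based result as well, but it is not what 11.2.1 or the lead-time objective says.

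**The effect is easily overstated.** This stands. A reader might infer that 3 of 11 relapses are affected. But 30% is a ceiling on HCG/AFP sensitivity, not the marker-first share, and at 6, 18 and 36 months markers and scans are scheduled together. For sensitivity, only marker-first relapses that are miRNA-negative at the marker date can change status. A reader might also infer a clear rise in false progression. Setting 3 of the 11 relapses at 85% or 90% and the other 8 at 75% gives P(go) of 0.258 or 0.292. Those inputs are assumed, and they imply mean sensitivity on the scan reference of (8 × 0.75 + 3 × 0.85)/11 = 77.7% or (8 × 0.75 + 3 × 0.90)/11 = 79.1%. They count as false progression only if the other reference is already taken as the right one.

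**Conclusion.** The inconsistency is real and should be removed. The protocol has two reference dates for one quantity, and they can disagree for a marker-first relapse whose scan comes more than 2 weeks after the marker.

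The expected effect on the go/no-go decision is small: under 1 of 11 relapses even with 30% marker-first and 75% sensitivity, and about 0.2 if sensitivity is the expected 95%. Any P(go) above 0.197 rests on assumed shares and conversion rates, so the documents do not support a claim that the error rate is materially inflated. It still matters because a single relapse separates 9/11 from 10/11, and because exposure is greatest when the assay is weak, which is when the rule must work.

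The lead-time effect is wider. It touches every marker-first relapse that miRNA detects before the scan, whether or not sensitivity is high. A reader might infer that each such lead time is overstated by the marker repeat plus the scan wait. The documents do not support that for real-time samples, where a positive miRNA triggers the scan directly. Nor does the protocol say that detection is dated at the first raised marker; it leaves that open.

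**What to change.** - In 11.1.1, 11.3.1 and 11.3.2, use the 11.2.1 reference: the first detection, by imaging or another standard component, that led to the imaging-confirmed relapse, with the 2-week window counted from that date.
- State once whether a marker detection is dated at the first raised sample or the confirming sample. Either can be defended. The choice should be fixed before outcomes are known, bearing in mind that section 1.1.2 says LDH lacks specificity.
- In 11.2.2 and 11.3.3, define lead time against the same date, and report lead time to the scan as supplementary.

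This is a change of wording. The 10/11, 19/21 and 26/28 thresholds and the sample size stay. Marker and scan dates follow from the scheduled assessments. Physical examination after registration is optional under section 7.2.1, so if an examination finding is to count as a detection, the sponsor should check that its date is captured. The cost is that sensitivity and lead time may come out slightly less favourable.

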7.2. Surveillance Assessments

7.2.1. PART A

The following assessments should be conducted at the time points indicated. For scheduling purposes, a 2-week window either side of the actual time point is acceptable. Imaging should be performed within 2 weeks either side of the blood sample being taken for miRNA analysis.

3 months (m), 6m, 9m, 12m, 15m, 18m, 21m, 24m, 30m, 36m, 42m, 48m, 54m and 60m after registration in the trial.

- Routine tumour markers (AFP, β -HCG and LDH)
- Review/Reporting of SAEs as appropriate (see section 10)
- Collection of blood sample for miRNA analysis (except at 54m)* - described further in section 10
- **Required radiological assessments** (Ideally the same imaging modality should be used for surveillance throughout the trial.):
 - **For seminoma participants:** Cross-sectional abdominal imaging at 6m, 18m and 36m, preferably with MRI but CT can be used according to local practice.
 - **For dysgerminoma participants:** Cross-sectional abdominal+/-pelvic imaging at 6m, 18m and 36m, preferably with MRI. For participants under the age of 19, pelvic ultrasound (US) may be used at physician's discretion where MRI is not possible or where US is used routinely at site.
- **Additional imaging and assessments according to local practice:** In addition to the required radiological assessments above, the following can also be performed according to local practice:
 - cross-sectional imaging (abdominal+/-pelvic MRI or CT) can be performed at up to 4 further time points over the 5-year follow-up period
 - Physical examination
 - For seminoma, chest x-ray can be performed as per local practice
 - For dysgerminoma participants, low dose chest CT and transvaginal US can be performed as per local practice.
- Acceptability questionnaire to be completed by participant at 12m** (for participants 16 years old and over only)

*Note: miRNA samples taken at 9m, 15m, 21m and 42m will be analysed retrospectively in case of relapse only, and results will not be fed back to centres in real time.

**Note: Acceptability questionnaire (16 and over only) emailed or posted to participant's home address directly from ICR-CTSU, based on participant's preference, but site teams are asked to remind the participant about completion in order to maximise return rates.

7.3. Procedure for follow-up of positive routine tumour marker or finding on physical exam

[figure not shown]

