In the event that miRNA remains positive, but relapse has not been confirmed on imaging as part of the above process, this should also be discussed with the trial team to determine appropriate management on a case-by-case basis. Where no more surveillance imaging is scheduled (i.e. >36 months post-randomisation),

it may be appropriate to schedule a further imaging investigation 6 months after previous scan (i.e. approximately 9m after the first positive miRNA result).

Please note that the investigations detailed above are the minimum requirements for trial purposes; other investigations can be carried out on a case-by-case basis as deemed appropriate by the local investigator.

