9.1.1. PART A Sample scheduling

Blood samples for miRNA testing will be collected at all protocol-mandated visits, with the exception of the 54-month visit, timed from registration as follows: registration, 3 months (m), 6m, 9m, 12m, 15m, 18m, 21m, 24m, 30m, 36m, 42m, 48m, 60m.

Samples collected at registration, 3m, 6m, 12m, 18m, 24m, 30m, 36m, 48m and 60m will be analysed in real time and results fed back to the centre. Samples collected at the other time points will be analysed retrospectively at the end of Part A for participants who relapsed during the trial. Results from these samples will not be fed back but will be used to provide more detailed information of the potential lead time for relapse detection on miRNA when compared with imaging.

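### Required scans stop at 36 months but miRNA-triggered imaging continues, and the 26/28 rule has no per-participant cut-off, so late relapses bias sensitivity modestly upward

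*Protocol*

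**What the plan says.** **Reference imaging.** For seminoma, section 7.2.1 requires "Cross-sectional abdominal imaging at 6m, 18m and 36m, preferably with MRI but CT can be used according to local practice"; dysgerminoma has the same three time points. Up to four further cross-sectional scans over five years are allowed if local practice includes them. Section 7.4.2 treats the later period as one without planned scans: "Where no more surveillance imaging is scheduled (i.e. >36 months post-randomisation".

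**The test under evaluation.** Section 9.1.1: "Samples collected at registration, 3m, 6m, 12m, 18m, 24m, 30m, 36m, 48m and 60m will be analysed in real time". The 42-month sample is stored and analysed only for participants who relapse. Under section 7.4.2 a positive real-time result leads to MRI or CT with a repeat miRNA test, then PET-CT if that imaging is negative, then further follow-up.

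**The rule.** Section 11.1.1 plans two later looks at one-sided alpha 0.2, with aims of >80% at 21 relapses and >85% at 28. It states the pass marks as "requiring at least 19 of 21 and at least 26 of 28 relapses to be detected on miRNA". Section 11.3.1 applies these marks to the first 21 and first 28 relapses. It times the final look as "A final analysis will take place when all Part A participants have been followed up for 36 months", when 28 relapses are expected.

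**Who is counted.** Section 11.2.1 takes as denominator the relapses found through standard investigations. Section 11.3.2 includes every imaging-confirmed relapse with a miRNA test within two weeks of the imaging. Neither sets a limit at 36 months per participant.

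**The concern.** Up to 36 months, a relapse that miRNA misses will normally meet a required scan, so the miss becomes visible and is scored. After 36 months, whether a participant is imaged depends partly on the test being evaluated: a positive result brings a scan, a negative one does not. This is differential verification, and it raises apparent sensitivity. A relapse found through a positive miRNA result also meets the section 11.3.2 inclusion condition easily, because section 7.4.2 asks for a repeat miRNA test alongside the imaging.

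The final look carries the claim that sensitivity exceeds 85%, which section 11.1.1 names as the ultimate aim, and it informs whether Part B continues. The miRNA arm of Part B has no routine imaging, so it cannot expose misses in the same way. Part A is the trial's main direct evidence on sensitivity.

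**Working it through.** **Inputs**
- Rule: at least 26 of 28; null sensitivity 0.85; one-sided alpha 0.20; stated power above 80% (section 11.1.1).
- Alternative: "Sensitivity of miRNA for relapse detection is expected to be at least 95% based on previous studies" (section 11.1.1).
- HCG and AFP sensitivity for seminoma relapse: at most 30% (section 1.1.2). This motivates one of the scenarios below.
- Late relapses among the 28, called k: not given. Section 11.1.1 expects 12% of participants to relapse, nearly all by 36 months. If 5% to 10% of the 28 were late (assumption), k would be 28 × 0.05 = 1.4 to 28 × 0.10 = 2.8.
- Share v of late misses that surface by other routes: not given; assumed 0, 0.3 or 0.5.

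**Step 1: the plan's own figure.** With X ~ Binomial(28, p):
- p = 0.85: P(X ≥ 26) = 0.1243 + 0.0522 + 0.0106 = 0.187.
- p = 0.95: P(X ≥ 26) = 0.837.

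The rule reproduces: error below 0.20 and power above 0.80. The margin below 0.20 is only 0.013.

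**Step 2: upper bound (v = 0).** If no late miss ever surfaces, each late relapse in the count is a certain hit. Passing then needs at least 26 − k hits among 28 − k ordinary relapses:
- k = 1: P(X ≥ 25 | n = 27, p = 0.85) = 0.207
- k = 2: P(X ≥ 24 | n = 26, p = 0.85) = 0.230
- k = 3: P(X ≥ 23 | n = 25, p = 0.85) = 0.254

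**Step 3: some late misses surface.** Among late relapses that come to light, the proportion scored as hits is q = 0.85 / (0.85 + 0.15v):
- v = 0.3: q = 0.85 / 0.895 = 0.950
- v = 0.5: q = 0.85 / 0.925 = 0.919

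The pass probability is the sum over j = 0 to k of P(J = j) × P(X ≥ 26 − j), with J ~ Binomial(k, q) and X ~ Binomial(28 − k, 0.85).

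| Late relapses among 28 | v = 0 (bound) | v = 0.3 | v = 0.5 |
|---|---|---|---|
| 0 | 0.187 | 0.187 | 0.187 |
| 1 | 0.207 | 0.201 | 0.196 |
| 2 | 0.230 | 0.215 | 0.206 |
| 3 | 0.254 | 0.230 | 0.216 |

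One late relapse leaves the error close to 0.20. Two take it slightly above 0.20 in each scenario.

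**Step 4: would dropping late relapses outright be safe?** With 27 relapses, 25/27 has error 0.207, so alpha 0.2 forces 26/27 (error 0.072; power at 95% is 0.606). With 26 relapses, 24/26 has error 0.230, so 25/26 is needed (error 0.082; power 0.624). A hard exclusion that leaves fewer than 28 relapses would cut power from 0.837 to about 0.61–0.62.

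**The case against.** Several points on the other side are sound and limit the finding.

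- **The 42-month sample is not reported in real time.** Apart from follow-up of a positive result at or before 36 months, no scheduled miRNA result can prompt a scan until the 48-month sample. New relapses found between 36 and 48 months mostly surface independently of miRNA and can be scored either way. This stands and narrows the window.
- **Few participants are exposed.** At the final look a participant has a 48-month sample only if registered about 12 months before the last recruit, and a 60-month sample only if about 24 months before. A reader might infer that the earliest recruits are then near 60 months, but the protocol gives no recruitment length, so this is unsupported.
- **Misses can surface by other routes.** Optional local scans, marker visits at 42, 48, 54 and 60 months, and symptoms remain. A reader might infer that late relapses are near-automatic hits; that is only the v = 0 bound.
- **The denominator is unsettled.** On the strict wording of section 11.2.1, a relapse found only by a miRNA-triggered scan might not be counted at all. Section 11.3.2 would include it. The two sections do not resolve this, so the bias depends on the reading in section 11.3.2.
- **The consequence is limited.** Part A is largely descriptive, the IDMC also weighs secondary endpoints, and the 10/11 decision to open Part B, taken as recruitment closes, is probably little affected.

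A per-participant cut-off could also be left to the analysis plan. But the protocol itself fixes the endpoint, analysis set, timing and rule, and as fixed they admit the bias.

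**Conclusion.** The concern holds as a modest upward bias at the final look. Required imaging ends at 36 months, miRNA-triggered imaging does not, and the first 28 relapses are counted without a per-participant limit. At a true 85%, the false-pass probability is 18.7% with no late relapse. It is at most 20.7% with one and 23.0% with two, and about 19.6–20.1% and 20.6–21.5% if 30–50% of late misses surface. These figures rest on assumed values for the number of late relapses and for v, and on counting miRNA-triggered relapses as section 11.3.2 does.

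A reader might conclude that the rule plainly breaks its 20% error. The documents do not support that: with one late relapse the error sits near 20%, and few late relapses are expected.

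**What to change.** In sections 11.3.1 and 11.3.2, add for the final analysis:

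1. A pre-specified sensitivity estimate for the IDMC, limited to relapses detected up to and including the required 36-month scan, plus its window and any repeat of an equivocal 36-month scan.
2. If at least 28 such relapses exist, this estimate is used for the >85% claim, with the 26/28 rule unchanged and its error at 18.7%.
3. If fewer than 28 exist, this estimate is reported with its exact confidence interval beside the 26/28 result. No smaller pass rule replaces 26/28, given the loss of power shown above.
4. Later relapses are listed separately, stating whether a miRNA result prompted the imaging.

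Sections 11.2.1 and 11.3.2 should also say the same thing about relapses found only on miRNA-triggered imaging.

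The cost is a few sentences, no new data beyond the reason for each late scan, and slightly less precision if a few relapses leave the restricted count.
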